6.4.2 Orthostatic blood pressure

At visits where orthostatic BP and pulse are collected, supine and standing measurements should be made after the seated BP and pulse measurements have been made, using the same arm that was used for the seated BP measurements. All readings should be recorded. Ideally, blood pressure should be measured with the same machine, at the same time of day, and by the same personnel at each visit.

6.4.3 Supine BP and pulse

The supine BP and pulse must be measured prior to the standing BP and pulse. After the patient rests in the supine position for at least 5 minutes, supine BP and pulse will be determined from three replicate measurements obtained at least 1 minute apart. All three readings must be recorded. For study analyses, the average of the three BP and pulse readings will be used.

6.4.4 Standing BP and pulse

After the supine BP and pulse measurements are obtained, the patient will stand for 2 to 3 minutes. After this time, the BP will be measured with the arm supported at the level of the heart. Standing BP and pulse will be determined from three replicate measurements obtained at least 1 minute apart. All 3 readings must be recorded. For study analyses, the average of the three BP and pulse readings will be used.

If a new occurrence of previously absent orthostatic hypotension is demonstrated, it should be recorded as AE. The investigator may consider reducing concomitant anti- hypertensive medication to alleviate signs and symptoms of orthostatic hypotension.

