3 STUDY PLAN AND PROCEDURES

3.1 Study Design

Randomized, double-blind, placebo-controlled trial. The control group will receive placebo administered orally once daily for 12 weeks plus standard of care. The treatment group will receive dapagliflozin 10 mg administered orally once daily for 12 weeks plus standard of care. A follow-up visit at week 13 will be performed to evaluate markers of renal function.

3.2 Study Procedures

At the screening visit, participants will undergo a physical exam (including vital signs and weight assessment), a laboratory panel, including HbA1c, BNP, NTproBNP, and a renal panel will be performed to determine study eligibility (Table 1: Study Plan). At the randomization visit, participants will undergo a physical exam (including vital signs and weight assessment), laboratory testing, including HbA1c, BNP, NTproBNP, and a renal panel, complete the KCCQ, perform a 6 minute walk test and lung fluid volume will be measured with the SensiVest at selected sites. Treatment or placebo will be administered for 12 weeks, with follow-up visits at 6 and 12 weeks during which a physical exam (including vital signs and weight assessment), labs, KCCQ, a 6-minute walk test will be performed, lung fluid volume will be measured with the SensiVest (at selected sites), and AEs/SAEs will be recorded. On days 2 and 10, as well as weeks 4 and 9 participants will be contacted by phone to evaluate for AEs/SAEs, and encourage compliance with the study medication. One week after treatment ends, renal function will be evaluated and lung fluid volume will be measured with the SensiVest at a follow-up office visit (at selected sites).

Table 1: Study Plan

	12 -week double-blind treatment period									
	Screening	Randomization								
Visit	S	1	2	3	4	5	6	7	8	
Week ^{g)}	-2	0	2d	10d	4	6	9	12 ptdv	13	
Office Visit	Х	Х				Х		Х	Х	
Phone Visit ^{f)}			Х	Х	Х		Х			
Informed consent	Х									
Assess eligibility	Х	Х								
Physical Exam a)	Х	Х				Х		Х	Х	
Vital signs (BP, pulse)	Х	Х				Х		Х	Х	
Orthostatic BP, pulse	Х	Х				Х		Х	Х	
NYHA Class	Х	Х				Х		Х	Х	
Weight	Х	Х				Х		Х	Х	
Height	Х									
Body Mass Index (BMI) ^{m)}	Х	Х				Х		Х	Х	
Waist circumference	Х	Х				Х		Х	Х	
Medical History	Х									
Concomitant medication	Х	Х	Х	Х	Х	Х	Х	Х	Х	
Laboratory assessments	X ^{b)}	$X^{\mathrm{c},\mathrm{k})}$				X ^{c,k)}		$X^{c,k)}$	X d)	
Urine pregnancy test ^{e)}	Х	Х				Х		Х	Х	
Urine albumin/ creatinine ratio test ⁱ⁾	Х	Х				Х		Х	Х	

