6.3.2 Physical examination

A physical examination should be done according to schedule shown in Study Plan (Table 1).

- A complete physical examination should include general appearance, head, eyes, ears, nose, throat, neck, cardiovascular system, lungs, abdomen, lymph nodes, extremities, neurological system, skin, and musculoskeletal system. Collection of pulse and blood pressure should also be collected as described in section 6.4. The patient should always be evaluated for the presence of edema and other signs of volume overload (jugular venous distention, rales, ascites, etc).
- Evaluation of volume depletion, including orthostatic vital signs and other physical exam findings consistent with dehydration
- Evaluation for the presence of ketoacidosis, in patients experiencing signs or symptoms of ketoacidosis, such as tachypnea or hyperventilation, anorexia, abdominal pain, nausea, vomiting, lethargy, or mental status changes; administer appropriate testing for ketoacidosis and direct patients to the emergency department if ketoacidosis is confirmed.

• Baseline data are collected at Visit 1 and any new or aggravated findings discovered on subsequent physical examinations should be recorded as AE if clinically relevant.

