8.3.1 Collection of Adverse Events

AEs and SAEs (including hospitalizations for heart failure) will be recorded from Screening throughout the treatment period and including the follow-up period (Visit 8).

All AEs/SAEs are to be recorded by the site. SAEs, DAEs and AEs of Special Interest will be captured in the e-CRF. Non-serious AEs will not be captured in the e-CRF.

SAEs are defined in section 8.2.

A drug adverse event (DAE) is an adverse event which leads to premature and permanent discontinuation of study medication.

AEs of Special Interest will include DKA, volume depletion (defined as hypotension, syncope, orthostatic hypotension or dehydration) and severe hypoglycemic events.

Information about all urgent outpatient heart failure visits will also be recorded by the site and captured in the e-CRF.

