8.3.6 Adverse Events based on examinations and tests

The results from protocol mandated laboratory test and vital signs will be summarized in the clinical study report. Deterioration as compared to baseline in protocol-mandated laboratory values and vital signs will only be reported as AEs if they are clinically significant, fulfill any of the SAE criteria or are the reason for discontinuation of treatment with the investigational product, or require the patient to receive specific corrective therapy.

If deterioration in a laboratory value/vital sign is associated with clinical signs and symptoms, the sign/symptom will be reported as an AE and the associated laboratory result/vital sign will be considered as additional information. Wherever possible the reporting investigator uses the clinical, rather than the laboratory term (e.g., anemia versus low hemoglobin value). In the absence of clinical signs or symptoms, clinically relevant deteriorations in non-mandated measurements will be reported as AE(s).

Any new or aggravated clinically relevant abnormal medical finding at a physical examination as compared with the baseline assessment will be reported as an AE.

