3.3 Physical examination

- Body Mass Index
- Sitting Pulse and Blood Pressure
- Supine Pulse and Blood Pressure
- Standing Pulse and Blood Pressure

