6 SAFETY ANALYSES

Safety analyses will be performed on the safety analysis set (SAF). Total number of adverse events as well as number and proportion of patients developing adverse event(s) will be compared by treatment group. For patient level analyses multiple events will be counted once only per subject in each summary. The following safety variables will be included:

- 1. All cause death
- 2. Cardiovascular death
- 3. Non-fatal myocardial infarction (MI)
- 4. Stroke
- 5. Acute kidney injury (defined as doubling of serum creatinine based on the modified RIFLE criteria)
- 6. Adverse events (AEs).
 - Adverse events of special interest
 - o Diabetic Ketoacidosis
 - Volume Depletion Event (defined as hypotension, syncope, orthostatic hypotension or dehydration)
 - Severe Hypoglycemic Event
 - o Lower Limb Amputations
 - Drug Adverse Event
 - Serious Adverse event
 - $\circ \quad \text{Resulted in death} \quad$
 - In-patient hospitalization or prolonging of existing in-patient hospitalization

- Persistent or significant disability
- Life-threatening
- Congenital anomaly/birth defect
- Important medical event

Safety analyses will be restricted to adverse events that occurred between randomization and 12 weeks. Adverse events occurred between 12 weeks and 13 weeks will be presented separately in a supplemental analysis.

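### Protocol 6.4.4 and 8.3.6 disagree on whether a new, asymptomatic, clinically insignificant orthostatic fall is an adverse event, and the SAP derives no orthostatic event from the recorded pressures

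*Protocol*

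**What the plan says.** Protocol Table 1 schedules "Orthostatic BP, pulse" at screening, randomization and weeks 6, 12 and 13. Sections 6.4.3 and 6.4.4 require three supine and three standing readings each time and say that their averages are meant for the study's analyses.

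Three passages say when a finding becomes an adverse event:

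- Section 6.4.4, on orthostatic hypotension specifically: "If a new occurrence of previously absent orthostatic hypotension is demonstrated, it should be recorded as AE".
- Section 8.3.6, on mandated laboratory values and vital signs generally: "Deterioration as compared to baseline in protocol-mandated laboratory values and vital signs will only be reported as AEs if they are clinically significant". The sentence goes on to three alternatives: an SAE criterion is met, the change is the reason treatment stops, or it needs specific corrective therapy. Where clinical signs or symptoms accompany the change, "the sign/symptom will be reported as an AE and the associated laboratory result/vital sign will be considered as additional information".
- Section 6.3.2, on physical examination: "any new or aggravated findings discovered on subsequent physical examinations should be recorded as AE if clinically relevant".

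Section 8.3.1 lists as an event of special interest "volume depletion (defined as hypotension, syncope, orthostatic hypotension or dehydration"). It restricts the e-CRF to serious events, events that permanently end study treatment, and events of special interest. SAP section 6 analyses the same item, "Volume Depletion Event (defined as hypotension, syncope, orthostatic hypotension or dehydration"), as counts of reported events and of patients with events. The SAP names "Standing Pulse and Blood Pressure" only among baseline characteristics (3.3). After baseline, the only pressure variable it names is supine systolic pressure, a secondary efficacy endpoint (2.4, 5.2).

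**The concern.** A standing pressure taken at a study visit is a protocol-mandated vital sign, so both 6.4.4 and 8.3.6 apply to it. One section has no condition and the other says only. Neither refers to the other or says which prevails.

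In many trials this would matter little, because every adverse event reaches the database and can be regrouped later. Here the e-CRF filter in 8.3.1 means that a site's choice of rule can decide whether a non-serious case exists in the analysis data at all. Up to 30 centers make that choice, without a numeric definition to standardise it.

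The component is not a peripheral one. Section 1.4.2 names volume depletion as a potential concern, 8.2.11 says the risk is greater when two diuretics are combined, and 12.2.4 lists it among the safety variables chosen in advance. If the count is incomplete, a low figure may be taken as more reassuring than it is.

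**Working it through.** The plan gives no figure to reproduce on this point, so the check sets the passages side by side for each kind of new postural fall.

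| New orthostatic fall | Under 6.4.4 | Under 8.3.6 | Agreement |
|---|---|---|---|
| Clinically significant, serious, treatment-stopping or needing corrective therapy; no separate symptom | AE | AE | Yes |
| Asymptomatic, not clinically significant, no action needed | AE, hence of special interest and in the e-CRF | Not an AE, so no event in the e-CRF | No |
| Accompanied by a symptom such as dizziness | AE, termed orthostatic hypotension | AE, but one sentence makes the symptom the event | Both give an AE; the term is in some doubt |

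The second row is a direct contradiction. The clinical-relevance condition in 6.3.2 points the same way as 8.3.6.

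The third row is a matter of terminology. Section 8.3.5 prefers a diagnosis to a list of symptoms, and 8.3.6 prefers the clinical term to the laboratory term. Both favour recording orthostatic hypotension. If a site nevertheless recorded only a non-serious symptom that is outside the special-interest list and did not end study treatment, 8.3.1 would keep it out of the e-CRF.

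**Effect on the count.** For one arm, let p be the true proportion with new orthostatic hypotension, q the share of those cases in the second row, and s the share of patients at sites that follow 8.3.6. Assume that s does not depend on case type and that all other cases are captured. Then

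counted proportion = p × (1 − s × q).

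The factor is 1 if q = 0, whatever s is. If q = 1, it is 0.75, 0.50 and 0.25 for assumed s of 0.25, 0.50 and 0.75. The documents give no value for p, q or s, so they do not locate the factor within this range. If s and q are equal in the two arms, the factor cancels from the risk ratio, and the absolute difference shrinks by the same factor.

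**Use of the readings.** Weeks 6 and 12 give 2 visits × (3 supine + 3 standing) = 12 pressure readings per patient on treatment. The protocol means them to be used: 2.1.3 includes blood pressure in the safety assessment, 6.4.3 and 6.4.4 refer to study analyses, and 8.3.6 promises a summary of mandated vital signs in the study report. SAP section 6 contains no blood pressure variable. The SAP nowhere derives a post-baseline supine-to-standing change or an orthostatic event.

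**The case against.** The strongest reply is that 6.4.4 is a specific instruction about one named condition and so overrides the general rule in 8.3.6. That reading is reasonable, but no text states it, and the word only in 8.3.6 works against it.

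A second reply is that any fall omitted under 8.3.6 was, by that rule, not clinically significant and needed no action, and that the composite has three other components. This stands as a limit on importance. It does not make the count consistent between sites.

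A reader might also infer stronger things that the documents do not support:

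- *That the two rules conflict for all orthostatic hypotension.* They agree whenever the fall is clinically significant, serious, treatment-stopping or in need of corrective therapy and has no separate symptom. Section 6.4.4 itself contemplates a reduction of antihypertensive medication, and a case handled that way plausibly meets the corrective-therapy condition.
- *That symptomatic falls disappear as dizziness.* This requires reading one sentence of 8.3.6 without 8.3.5 and without the preference for clinical terms.
- *That the measured pressures are never used.* Section 6.3.2 has sites assess volume depletion with orthostatic vital signs, and in 6.4.4 the readings trigger the event. What is missing is a numeric definition and a planned analysis.
- *That the treatment comparison is biased.* Sites and patients are blinded, and nothing in the documents shows that the choice of rule or the mix of cases differs by arm.

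**Conclusion.** The contradiction is real but narrow. It concerns new orthostatic falls that are asymptomatic, not clinically significant and need no action, with a lesser doubt about the term used for symptomatic falls. Its consequence is a volume-depletion count that can be incomplete and inconsistent between sites. The size cannot be derived from the documents, because they give neither a rate of orthostatic hypotension nor the share that sites would judge insignificant. In particular, they do not support the inference that 8.3.6 would remove nearly all non-serious cases, since clinically significant and treated ones are still reported under it.

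The second part rests on the text alone. The protocol collects the readings and intends them for analysis and reporting, but neither document defines orthostatic hypotension numerically and the SAP plans no post-baseline postural summary. Deriving the event from the readings would apply one criterion to every patient measured, whichever reporting rule the site followed.

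**What to change.** 1. Reconcile Protocol 6.4.4 and 8.3.6. State which governs orthostatic hypotension found at a visit, and how a fall with symptoms is to be termed so that its special-interest status is clear. The choice of rule is the sponsor's.
2. In SAP section 6, pre-specify a table for the safety set, by arm, at weeks 6 and 12. It should give the supine-to-standing change and the proportion with new orthostatic hypotension (absent at baseline), both derived from the averaged readings already recorded. The sponsor should fix the numeric criterion before unblinding. Show the table next to the volume-depletion count from reported events.

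The cost is a clarifying sentence and one extra table, with no new measurement. The reported count may be higher, and showing both sources side by side lets a reader see how far they differ.

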6.5 Six Minute Walk Test (6MWT)

The 6MWT is a practical simple test that requires a 100-ft hallway but no exercise equipment or advanced training for technicians. Walking is an activity performed daily by all but the most severely impaired patients. This test measures the distance that a patient can quickly walk on a flat, hard surface in a period of 6 minutes (the 6MWD). It evaluates the global and integrated responses of all the systems involved during exercise, including the pulmonary and cardiovascular systems, systemic circulation, peripheral circulation, blood, neuromuscular units, and muscle metabolism. It does not provide specific information on the function of each of the different organs and systems involved in exercise or the mechanism of exercise limitation, as is possible with maximal cardiopulmonary exercise testing. The self-paced 6MWT assesses the submaximal level of functional capacity. Most patients do not achieve maximal exercise capacity during the 6MWT; instead, they choose their own intensity of exercise and are allowed to stop and rest during the test. However, because most activities of daily living are performed at submaximal levels of exertion, the 6MWD may better reflect the functional exercise level for daily physical activities.¹²

6.6 SensiVest Measurement of Lung Fluid Volume

SensiVest utilizes remote dielectric sensing ReDS[™] technology, to estimate lung fluid volumes. The technology has been adapted from the military (which used it to see inside buildings and to find survivors among rubble). Sensible Medical has adapted the same principles and created a vest that when worn sends low-power electromagnetic energy through the lungs, which decipher air content from fluid. At selected DEFINE-HF study sites, patients' lung fluid volume will be measured at rest (prior to 6 minute walk test) during randomization (0 weeks), 6, 12 and 13 weeks. These results will be uploaded to a secure web portal and all data entry will be handled in a de-identified and blinded fashion by the National Coordinating Center. The local site study staff will be blinded to the SensiVest results at all times. A subset of sites may offer NYHA class III patients the option to use SensiVest at home and readings may be taken by these patients twice a day for the 13 weeks, once in the morning (when a patient wakes up) and once at night (when a patient lies down to sleep).

6.7 Collection of Kansas City Cardiomyopathy Questionnaire (KCCQ)

The KCCQ (see appendix B) is a disease-specific health status instrument composed of 23 items that quantify the domains of physical limitation, symptoms, self-efficacy, social limitation, and quality of life limitation from heart failure. The overall summary score and all domains have been independently demonstrated to be valid, reliable, and responsive to clinical change. Scores range from 0 to 100. For the KCCQ overall summary score, a small but clinically meaningful change is
considered to be \geq 5 points.¹³ The patients will fill in PRO (KCCQ) paper form under the supervision of the site staff.

6.8 Laboratory assessments

Blood and urine samples for determination of clinical chemistry, hematology, urinalysis and biomarker testing will be taken at the times indicated in the Study Plan (see Table 1). Any additional laboratory safety samples taken at the investigator's discretion will be analyzed locally.

It is recommended that patients do not have their baseline diuretics changed based upon naturietic peptide levels, and that the patient's primary cardiologist be blinded to the BNP and NTproBNP data collected throughout the trial. There have been varying results with trials of NTproBNP guided clinical management of heart failure. Two randomized clinical trials have shown no clear benefit.²³⁻²⁴ Given the uncertainty of benefit, neither serial collection nor treatment based upon NTproBNP levels are currently endorsed by ACC/AHA guidelines.²⁵ For these reasons, it is recommended that heart failure medication changes not be made based on naturietic peptide levels. If a patient is clinically symptomatic or endorses signs or symptoms of volume overload, clinical judgment should be used and diuretic adjustments made as warranted.

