6.2 Data Collection at enrollment and follow-up

TABLE 3 Laboratory variables

Visit	S	1	2	3	4	5	6	7	8
Week	-2	0	2d*	10d*	4	6	9	12	13
HbA1c	Х	Х				Х		Х	
Glucose (included in the renal panel)		Х				Х		Х	
BNP	Х	Х				Х		Х	
NTproBNP	Х	Х				Х		Х	
Urine albumin creatinine Ratio	Х	Х				Х		Х	Х
Urine Pregnancy Test	Х	Х				Х		Х	Х
CBC		Х				Х		Х	
Renal Panel**	Х	Х				Х		Х	Х
Biomarkers***		Х				Х		Х	

*days after randomization

** The renal panel includes albumin, BUN/Creatinine Ratio (calculated), calcium, carbon dioxide, chloride, creatinine, estimated glomerular filtration rate (calculated), glucose, phosphate (as phosphorus), potassium, sodium, urea nitrogen

*** uric acid, IL-6, HS-CRP, CML, sRAGE, Gal-3, sST2 and hs-cTnT

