7 BIOLOGICAL SAMPLING PROCEDURES

7.1 Volume of blood

The total volume of blood that will be drawn from each patient for this study is listed in Table 4 below. The collection of additional samples is performed locally at the discretion of the investigator and recorded in the eCRF as appropriate, thus requiring additional sample volumes.

Assessment	Sample volume	Number of	Total Volume (mL)
	(mL)	Samples	
HbA1c	4 mL whole blood	4	16 mL
Glucose	2 mL whole blood	3	6 mL
BNP	2 mL whole blood	4	8 mL
NTproBNP	2 mL whole blood	4	8 mL
CBC	4 mL whole blood	3	12 mL
Renal Panel/Uric	4 mL whole blood	5	20 mL
Acid			
Biomarkers (IL-6,	40 mL whole	3	120 mL
HS-CRP, CML,	blood		
sRAGE, Gal-3,			
ST-2 and hs-cTnT)			
Total			190 mL

Table 4 Volume of blood to be drawn from each patient

7.2 Handling, storage and destruction of biological samples

Blood and urine samples will be processed by local staff for shipment to the central laboratory (Quest Diagnostics). All samples should be taken by adequately trained study personnel and

handled in accordance with instructions in the central laboratory manual. Up to date reference ranges will be provided during the study and laboratory results will be compared to the laboratory standard normal ranges and flagged if they are outside the normal range. The Investigator should make an assessment of any clinically significant abnormalities in the laboratory reports. The laboratory reports should be signed, dated and retained at the study site as source data for laboratory variables.

The clinical chemistry, hematology, and urinalysis samples will be disposed after analyses. The residual biomarker samples will be stored as described in appendix C.

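### Masking of BNP and NT-proBNP after randomization is only recommended, and only for the primary cardiologist; the protocol does not keep these values off the laboratory reports that investigators review

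*Protocol*

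**What the plan says.** Protocol 6.8 recommends that baseline diuretics not be changed on natriuretic peptide levels and that "the patient's primary cardiologist be blinded to the BNP and NTproBNP data collected throughout the trial". It repeats the advice for heart failure medication in general, and notes that neither serial measurement nor NT-proBNP-based treatment is endorsed by the guideline it cites. All of this is worded as recommendation. The investigator and site staff are not mentioned.

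Protocol 7.2 sends samples to a central laboratory. During the study, "laboratory results will be compared to the laboratory standard normal ranges and flagged if they are outside the normal range". It continues: "The Investigator should make an assessment of any clinically significant abnormalities in the laboratory reports". And then: "The laboratory reports should be signed, dated and retained at the study site as source data for laboratory variables". BNP and NT-proBNP appear in the table in Protocol 6.2 ("TABLE 3 Laboratory variables") at screening and at weeks 0, 6 and 12.

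For the exploratory lung fluid measure the rule is firm. Protocol 6.6 says: "The local site study staff will be blinded to the SensiVest results at all times". Protocol 5.5.1 deals with masking of treatment allocation and does not mention laboratory results.

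**The concern.** NT-proBNP is the whole of the first primary endpoint and one of the two components of the second. If an investigator sees a high week-6 value, diuretics or other heart failure drugs may be changed before week 12. If dapagliflozin lowers NT-proBNP, high values will be more common on placebo and so will such changes, which would pull the week-12 means together. The allocation blind does not prevent this, because the clinician reacts to the value and not to the arm.

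Protocol 4 recruits from general cardiology and heart failure clinics, so the investigator and the treating cardiologist may be the same person. In that case the recommendation to blind the cardiologist conflicts in practice with the instruction to review and sign the report. The plan requires masking of site staff for an exploratory measure and only advises a narrower form of it for the primary biomarker.

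**Working it through.** **Reading the documents together**

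1. *Who is masked, and how firmly.* Protocol 6.8: the primary cardiologist, as a recommendation. Protocol 6.6: all local site staff, as a rule, for SensiVest only.
2. *Who receives results.* Protocol 7.2: the investigator, for laboratory reports in general. Protocol 6.2 counts BNP and NT-proBNP among the laboratory variables. No section removes them from the reports after randomization. That they are printed is an inference from these two sections; neither document says so.
3. *Whether treatment can change between the visits.* Protocol 6.3.1 and 6.3.3 allow loop diuretic adjustment on review of weight and volume status, including at the week-9 phone visit. Protocol 6.8 allows it on symptoms or signs.
4. *Whether the analysis deals with it.* SAP 2.1 uses the last data before home inotropes, an assist device, transplant or an open-label SGLT-2 inhibitor. Diuretic and other heart failure drug changes are not on that list. SAP 2.4 and 5.3 treat loop diuretic dose as an exploratory outcome.

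**Possible size**

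The plan gives no figure to reproduce, and nothing in it fixes the size. The inputs below are assumptions.

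- True dapagliflozin/placebo ratio R = 0.85 at both visits.
- A fraction q of placebo patients is intensified after week 6 (10-30%), and their week-12 NT-proBNP falls by a fraction d (10-20%).
- On dapagliflozin the fraction is q′, taken as 0 in the first two rows.

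Week-6 results cannot change week-6 values, so only week 12 moves:

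week-12 ratio = R × (1 − q′d) / (1 − qd)

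SAP 5.1.1 defines the primary effect as exp(β1 + β3/2), the geometric mean of the two visit ratios:

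average ratio = √(R × week-12 ratio)

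Loss on the ratio scale = (average ratio − 0.85) / 0.15. Loss on the log scale = ln(average ratio / 0.85) / ln(1 / 0.85).

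| q, q′, d | Week-12 ratio | Average ratio | Loss, ratio scale | Loss, log scale |
|---|---|---|---|---|
| 0.10, 0, 0.10 | 0.85/0.99 = 0.859 | 0.854 | 3% | 3% |
| 0.30, 0, 0.20 | 0.85/0.94 = 0.904 | 0.877 | 18% | 19% |
| 0.30, 0.25, 0.20 | 0.85 × 0.95/0.94 = 0.859 | 0.855 | 3% | 3% |
| equal rates | 0.850 | 0.850 | 0% | 0% |

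The multiplier 1 − qd is an arithmetic-mean approximation. With (1 − d)^q instead, the second row gives 0.8^0.3 = 0.935 and an average ratio of 0.85/√0.935 = 0.879, which is hardly different.

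**The case against.** Four objections carry weight.

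- *Printing on site reports is not stated.* Protocol 7.2 speaks of laboratory reports in general, and Protocol 14 leaves details of specimen collection and processing to the central laboratory manual. That manual may already suppress these analytes. This stands: a reader might infer that sites are shown the primary endpoint, but the documents support only that the protocol does not say it is withheld.
- *The protocol advises against the behaviour feared.* It does so for diuretics and again for heart failure drugs. This stands as mitigation. It is advice, however, and no section asks sites to record whether a drug change followed a peptide value.
- *Co-intervention is observable.* Concomitant medication is recorded at every visit (Protocol Table 1 and 5.7.1), and SAP 5.3 compares loop diuretic dose between arms. This would help reveal the problem but would not repair the primary estimate.
- *The KCCQ route is weak.* A reader might infer that the KCCQ is biased because patients complete it on a "paper form under the supervision of the site staff". Supervision is not evidence of influence. The patient gives the answers, allocation is blinded, no section says peptide results are given to patients, and shipped samples should not have results back at the same visit. What remains is an indirect effect of week-6 results on the week-12 KCCQ, mainly through changed treatment.

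A reader might also infer that about a third of the effect could be lost. The second row at week 12 alone gives (0.904 − 0.85)/0.15 = 36%. The primary endpoint averages weeks 6 and 12, and that row assumes no intensification at all on dapagliflozin. Clinicians blinded to allocation would react to high values in both arms.

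**Conclusion.** The point holds as a gap in masking that is cheap to close. It is not a demonstrated bias. Masking of the primary biomarker is advisory and limited to one role, while the report-review section states no exception for it. The likeliest consequence is some dilution of the NT-proBNP contrast, although the documents do not establish the direction.

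The loss of about 3-19% rests on three assumptions: a ratio of 0.85 at both visits, intensification on placebo only, and the stated ranges for its frequency and its effect. With intensification in both arms the loss shrinks, and at equal rates it vanishes. Reactions to week-0 values precede treatment and should balance by randomization, so they are not counted.

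**What to change.** State in Protocol 6.8 and 7.2 that the central laboratory withholds week 0, 6 and 12 BNP and NT-proBNP from site reports until database lock and sends them only to the coordinating center, matching the masking of site staff already required for SensiVest. Keep screening values visible, because eligibility depends on them. Leave clinically indicated local testing unrestricted. Adjust the sign-and-retain wording in 7.2 so that the withheld results have a defined source record. If the laboratory manual already does this, the protocol should say so.

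The cost is a change to the laboratory report configuration and a small change to the source-data wording. Sites would not see serial trial values, but Protocol 6.8 itself recommends against acting on them.
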